Based on the above, this study protocol aims to design a three-stage 15 weeks intervention program, based on the guide to designing interventions of the behavior change wheel model (14), which includes both nutritional and sustainability elements, in the sense of considering unsustainable dietary behaviors of the Mexican population, in addition to taking into account their social, cultural and economic aspects. In addition to these axes, the basis of behavioral modification intervention programs is psychology. Therefore, it is proposed to design a sustainable-psycho-nutritional intervention program, whose objective is to promote the adherence of the population to sustainable diets. But, in addition, it is proposed to evaluate its effects on environmental indicators, metabolic biomarkers, and gut microbiota, as well as clinical aspects and body composition in a Mexican population sample. Because of the effectiveness of technologies use in nutritional (18,19) and environmental (20,21) interventions,

the intervention program will be a digital one, for which a mobile application is being designed to evaluate and monitor the intervened population. Therefore, this will be a m-Health intervention program.

We hypothesized that a sustainable-psycho-nutritional intervention digital program can modify the eating behavior of a Mexican population group and guide it towards a sustainable diet, generating decreases in glucose levels, total cholesterol (TC), LDL cholesterol (LDL-C), and triglycerides (TG), and increases in HDL cholesterol (HDL-C) levels. Likewise, we hypothesized that this type of program can modify the composition of the gut microbiota of the population, promoting the proliferation of bacteria related to metabolic health; reduce the water and carbon footprint of the sample's diets; maintain adequate body fat levels in the population with an adequate body fat percentage or reduce them in the overweight or obese population; maintain blood pressure levels in the healthy population and lower them in the population with high blood pressure, and reduce the presence of acanthosis nigricans.

2. Methods

It is proposed to carry out a quasi-experimental longitudinal study of three stages that will be related to each other.

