2.2.2 Procedure

Participants will be evaluated following the nutritional care process model (44). The first evaluation will be performed at the beginning of the intervention at baseline, and according to individual requirements, the behavioral objectives will be individually adapted and will be addressed for 7 weeks, considering 2 objectives per week, thus providing 2 weekly educational workshops. Also, personalized food plans will be prescribed, according to the linear programming optimization (29,30) performed at MATLAB®.

After 7 weeks of educational and nutritional intervention, at week 8, the experimental population will be divided into two sub-groups, where one group will stop being intervened completely (n = 25), and another will continue to receive messages through the mobile application (n = 25) for 8 weeks. Finally, at week 15, a final evaluation will be carried out. The study design is shown in Figure 2. Participants will be evaluated in the regard of Anthropometric, Biochemical, Clinical, Dietetics, Environmental, Socioeconomic level and cultural aspects,

Nutritional-sustainable knowledge, Behavioral aspects, and Physical activity (ABCD-ESNBP). These aspects will be evaluated according to the nutritional care process model, thus identifying the problem of the population, establishing the etiology, and stating the signs and symptoms (44).

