2.2.3 Sustainable-psycho-nutritional indicators

The ABCD-ESNBP indicators will be included in a complete clinical history that will be uploaded to the mobile application (Supplementary Material 3) and will be evaluated as follows: A) Anthropometric: height with a Smartmet® stadiometer, weight, and body composition (percentage of body fat, muscle mass, visceral fat) with an Omron® bioimpedance scale (HBF-511T-E/HBF-511B-E), $BMI = \text{weight}/\text{height}^2$, waist and hip circumference using a Lufkin® metal tape measure. The assessment will be performed following the validated techniques of Suverza and Haua (45).

B) Biochemical: glucose and lipid profiles (TC, LDL-C, HDL-C, and TG) will be determined through blood samples that will be taken from the antecubital vein of each participant, following the protocol from the Mexican Health Secretary (46,47). Samples will be taken by specialists, after an overnight fast of 8 to 12 hours and will be centrifuged at 3500 rpm for 15 min to separate the serum. Samples will be aliquoted and stored at -20°C until the day of testing. Tourniquets, alcohol swabs, 10 mL syringes, and blood collection tubes will be required. Gut microbiota will also be analyzed, for which fecal samples will be collected in a sterile stool container using a sterile kit including gloves and a spatula that will be delivered to the participants. Once collected, the samples will be divided into aliquots and will be stored at -80 °C, following a method used for the Mexican population (4,48).

C) Clinical: a clinical history will be carried out, covering pathologies suffering, pathological family history, medicaments, and supplement use (Supplementary Material 3). Clinical signs of insulin resistance (acanthosis nigricans) will be evaluated by physical exploration, searching for hyperpigmentation and thickening of the skin with velvety, in visible flex areas (axilla, anterior ulnar area, and posterior and lateral region of the neck) (49). Signs of nutrient deficiencies or excess will also be evaluated in relation to hair, nails, mouth, tongue, edema, and mucous membranes appearance (45). Likewise, blood pressure will be evaluated with a Medstar® sphygmomanometer and following the Mexican normativity (50).

[figure not shown]

Figure 2. Study design for stage 2. Own elaboration.

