2.3.4 Statistical analyses

The distribution of the data will be analyzed with the Kolmogorov Smirnov test. Descriptive analysis will be performed, including means, standard deviations, and medians. Next, the effects of the program on the selected variables will be assessed by comparing them between evaluations and between groups with t-student tests for paired and unpaired data, respectively, if a normal distribution is found. For no normally distributed data, the Wilcoxon test (repetitive measures) and the U de Mann Whitney test (independent groups) will be used. For no categorical variables, the chi-squared test will be used. Correlation analyses will also be performed, considering Pearson correlation for normally distributed data and Spearman correlations for no normally distributed data. Likewise, simple, and multiple linear regression models will be carried out, as well as binary logistic regression analysis, to identify relationships and risks between variables. Statistical analysis will be performed at STATA V12® program.

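### The analysis section names no paired test for categorical outcomes, although it promises comparisons between evaluations; chi-squared applied as written to before/after acanthosis data would be too conservative

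*Combined protocol and SAP*

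**What the plan says.** The analysis plan is the single paragraph in section 2.3.4. Effects are to be assessed by "comparing them between evaluations and between groups with t-student tests for paired and unpaired data, respectively", if the data are normal. If they are not, "the Wilcoxon test (repetitive measures) and the U de Mann Whitney test (independent groups) will be used". The paired/independent split is therefore made twice for continuous data. The rule for the remaining variables is "For no categorical variables, the chi-squared test will be used", with no split. The paragraph also lists regression models, "as well as binary logistic regression analysis, to identify relationships and risks between variables".

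The binary outcome most directly affected is in the hypotheses at the end of section 1, where the programme is expected to "reduce the presence of acanthosis nigricans". Section 2.2.3 describes the measurement: "Clinical signs of insulin resistance (acanthosis nigricans) will be evaluated by physical exploration". No grading scale is given. Section 2.2.2 sets the times: "The first evaluation will be performed at the beginning of the intervention at baseline" and "Finally, at week 15, a final evaluation will be carried out".

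**The concern.** The wording assigns chi-squared to variables that are not categorical, which cannot be meant. Read as categorical, the sentence still leaves one of the two promised comparisons without a suitable method. Baseline and final acanthosis status come from the same person and are strongly related. Pearson chi-squared takes the two evaluations as independent samples, so its variance is wrong for paired data. With positive within-person correlation the variance is too large and the p-value too high.

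At stake is a stated hypothesis: a real reduction within the experimental group could be reported as no change. Yes/no items in the COM-B questionnaire (Supplementary Material 4) would meet the same gap if they are compared between evaluations. There is also a reporting risk, because the form of the test would be chosen after the data are seen.

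**Working it through.** **Inputs from the documents.** 50 participants per group (section 2.2.1); dropout that may exceed half (same section); removal of non-completers (Table SM2.1); a 25 + 25 split of the experimental arm at week 8 (section 2.2.2). Completer groups of about 25 or fewer are therefore realistic.

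**Assumptions.** Acanthosis is recorded as present or absent. Prevalence, resolution and new-case rates are invented for illustration, since the documents give none. Tests are two-sided at 0.05. The plan states no figure for a categorical outcome, so there is nothing to reproduce first.

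**Formulas.** Let n be the number of people, b those who lose the sign, c those who gain it, p1 and p2 the proportions affected before and after, and p their average.
- Pearson on the two margins: X² = (p1 − p2)² / [p(1 − p)(2/n)].
- McNemar chi-squared: (b − c)² / (b + c).
- Exact McNemar: 2 × P(Binomial(b + c, ½) ≤ min(b, c)).

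**Worked example.** n = 50, 15 affected before, 9 after, b = 6, c = 0.
- Pearson: p = 24/100 = 0.24; X² = 0.12² / (0.24 × 0.76 × 0.04) = 0.0144 / 0.007296 = 1.97; p-value 0.160.
- McNemar chi-squared: 36/6 = 6.0; p-value 0.014.
- Exact McNemar: 2 × (½)⁶ = 0.031.

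The null variance that respects the pairing is (b + c)/n² = 6/2500 = 0.0024. Pearson uses 0.007296, about three times as much.

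**Two further tables.**
- n = 50, 20 before and 13 after (b = 8, c = 1): Pearson 0.0196/0.008844 = 2.22, p-value 0.137; McNemar 49/9 = 5.44, p-value 0.020; exact 2 × 10/512 = 0.039.
- n = 25, 10 before and 4 after (b = 6, c = 0): Pearson 0.0576/0.016128 = 3.57, p-value 0.059; McNemar 0.014; exact 0.031.

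**Power.** The rows with 40% resolving come from simulation with 20,000 runs each. Direct summation of the multinomial probabilities agrees with every row to within 0.01.

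| n | Baseline affected | Resolving | New | Pearson | Exact McNemar | McNemar chi-squared |
|---|---|---|---|---|---|---|
| 50 | 20% | 40% | 2% | 0.04 | 0.11 | 0.30 |
| 50 | 30% | 40% | 2% | 0.11 | 0.38 | 0.58 |
| 50 | 40% | 40% | 2% | 0.25 | 0.66 | 0.80 |
| 25 | 40% | 40% | 2% | 0.09 | 0.16 | 0.46 |
| 25 | 30% | 50% | 1% | 0.13 | 0.14 | 0.46 |

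The contrast depends heavily on the scenario. With half resolving and 1% new at n = 50, Pearson and exact McNemar have power 0.34 and 0.67 at 30% baseline, but 0.03 and 0.03 at 10% baseline.

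**Direction of error.** With no net change (15% of cases resolving, matched by new cases; n = 25 and 50; baseline 20-40%), the rejection rate was at most 0.0002 for Pearson, 0.006-0.047 for McNemar chi-squared and at most 0.013 for exact McNemar. Pearson's fault here is missed change.

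**The case against.** A reader might infer that the plan commits itself to Pearson chi-squared on a baseline-versus-final table. It does not say so. It names neither the form of the test nor the comparison; chi-squared may be meant for between-group use, where it is proper, and McNemar's test is itself of chi-squared type. The authors clearly know the paired/independent distinction. This stands as a limit on the claim: what the text shows is that no paired categorical method is specified. An unqualified reference to the chi-squared test would still normally be taken as Pearson's, and the paragraph promises both comparisons.

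A reader might also say that chi-squared is the only method available for binary outcomes. That is too strong, because binary logistic regression is listed. It is listed for relationships and risks, however, and in ordinary form it too assumes independent observations, so it does not supply the missing paired test.

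Reading the sentence as a plan to run chi-squared on continuous variables is not credible either. The same paragraph writes no normally distributed for non-normally distributed, so this is a copy-edit.

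Finally, the stake is modest. Acanthosis is last in a long list of hypotheses and absent from the stage 3 outcomes in the abstract. At about 25 people, or at low prevalence, exact McNemar gains almost nothing over Pearson. Both points stand and limit the size of the problem. Neither makes an independent-samples test valid for paired data.

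**Conclusion.** The point holds in a limited form. The sentence on categorical data is garbled, and no paired categorical test is named although comparisons between evaluations are planned. If Pearson chi-squared is applied to before/after acanthosis status, the p-value is wrong and too conservative. In the n = 50 scenarios with 40% resolving and 2% new cases, Pearson reaches roughly a third of the power of exact McNemar. With the 25-person scenario of 30% affected, half resolving and 1% new, the exact test has no useful advantage; McNemar chi-squared does (0.46 against 0.13). All these sizes rest on assumed rates and on a present/absent reading of acanthosis, and none should be quoted as the trial's actual loss. The sentence should be corrected before analysis; the design is not affected.

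**What to change.** Replace the sentence in section 2.3.4 with: *For categorical variables, groups will be compared with the chi-squared test (Fisher's exact test when an expected count is below 5), and evaluations within a group with McNemar's test (exact or mid-p when discordant pairs are few).*

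Add that the conclusion on acanthosis nigricans rests on the between-arm comparison at the final evaluation, by logistic regression adjusted for presence at baseline, and state how the two experimental sub-groups formed at week 8 enter that comparison. State also that acanthosis is recorded as present or absent, or give the grading used.

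The cost is a few lines of text, with standard tests and no new data or visits. One small downside is that exact McNemar has little power at about 25 per group, so the within-group result should be labelled supportive only. With few cases the adjusted model may also be unstable, so the counts by arm and evaluation should be reported beside it.

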2.4 Ethical and biosafety considerations

This project has been already evaluated and approved by the Ethics Committee of the Center for Studies and Research in Behavior, of the University Center for Biological and Agricultural Sciences (CUCBA) from the University of Guadalajara with the number CUCBA/CEIC/CE/002/2022 and by the Technical Research Committee of the University Center of the South (CUSUR), with the number 2021D001. This protocol will also be registered on Clinical Trials.gov. When performing the intervention, the Declaration of Helsinki (82) and biosafety protocols of the Secretary of Health of Mexico (83) will be followed all the time. All participants will sign an informed consent (Supplementary Material 7) and their identities will be protected by the Federal Law on Protection of Personal Data Held by Private Parties (84).

Both due to regulations in research with human beings, and due to the situation of the COVID-19 pandemic, a strict biosafety protocol will be followed, where mouth covers will be always worn, both by the evaluating staff and by the participants. Likewise, the sample collection personnel will wear protective glasses and sterile gloves and constant disinfection of the work area will be carried out. In addition, hazardous biological waste will be disposed of in a special trash can in accordance with the provisions of the Ministry of Health (85).

3. Discussion

By developing this program, we would be generating the first bases for the Mexican population (and future populations) to achieve a healthy and sustainable diet that can have positive effects on health outcomes and decrease the environmental impact of food consumption; thus addressing two of the main problems afflicting the

world population. Also, we are proposing a new concept: The Sustainable-Psycho-Nutrition, which is proposed as an approach based on behavioral science that integrates the psychological, social, cultural, economic, nutritional, and environmental aspects of eating behavior, whose objective is to generate the necessary bases to carry out behavioral change interventions, to guide the eating behavior of the population, towards sustainable eating behaviors. Within this term, we also launch the nutritional-ecological education, whose objective is to get people to acquire and perform the appropriate behavioral repertoire to determine what, how much, when, and how to eat, in relation to when, how much, and how energy is spent to maintain or recover their physical well-being, considering at all times the environmental impact of their behaviors and selecting the most sustainable foods, regarding the environment, culture, economy, preferences, food security, health, nutrition, among other factors (13).

Besides those aspects, the mobile application that we are currently developing is going to be a tool that will facilitate the promotion of sustainable diets first at the national level in Mexico, and forward, worldwide. Also, we will generate the first sustainable food guide for Mexico's context that will consider not only sustainability aspects but psychological and behavioral aspects. Moreover, the workshops, recipes, and food plans that we are creating are going to serve as tools for the health and environmental sector of the country to promote the consumption of sustainable diets. Finally, the link between gut microbiota and sustainable diets is a new aspect that this study will be characterized for the first time, specifically for the Mexican population. Finally, this project intends to bring attention to the importance of considering behavioral interventions and techniques for promoting sustainable diets.

References

2. Encuesta Nacional de Salud y Nutrición (ENSANUT). Encuesta Nacional de Salud y Nutrición [Internet]. 2018 [cited 2021 Jan 27]. Available from: <https://ensanut.insp.mx/encuestas/ensanut2018/informes.php>

Cardiovascular exercises (any including Walking, Jogging, Running, Aerobics, Zumba or dance, Cycling, Swimming)	Once a week	1
	2 times a week	2
	3 times a week	3
	4 times a week	4
	5 times a week	5
	6 times a week	6
	7 times a week	7
or		
Strength or resistance exercises (any including Crossfit, Weights, Multifunctional Focused exercises (for example, sit-ups, squats, push-ups)	< once a week	0
Combination of cardio and strength exercises	Once a week	1
	2 times a week	2
	3 times a week	3
	4 times a week	4
	5 times a week	5
	6 times a week	6
	7 times a week	7
	< once a week	0

Table SM1.2. Scores according to duration and intensity according to the type of physical activity

Type	Duration	Intensity	Score
Cardiovascular exercises (any including Walking, Jogging, Running, Aerobics, Zumba or dance, Cycling, Swimming)	Less than 10 minutes	Mild	0.5
	10 to 29 minutes	Mild	1
	30 to 59 minutes	Mild	2
	60 to 120 minutes	Mild	3
	More than 120 minutes, but less than 240 minutes	Mild	4
	More than 240 minutes	Mild	4 points and send a message not to exceed the amount of exercise
	Less than 10 minutes	Moderate	1
	10 to 29 minutes	Moderate	2
	30 to 59 minutes	Moderate	4
	60 to 120 minutes	Moderate	6
Strength or resistance exercises (any including Crossfit, Weights, Multifunctional Focused exercises (for example, sit-ups, squats, push-ups)	More than 120 minutes, but less than 240 minutes	Moderate	8
	More than 240 minutes	Moderate	8 points and send a message not to exceed the amount of exercise
	Less than 10 minutes	Intense	2
	10 to 29 minutes	Intense	4
	30 to 59 minutes	Intense	8
	60 to 120 minutes	Intense	12
	More than 120 minutes, but less than 240 minutes	Intense	16
	More than 240 minutes	Intense	16 points and send a message not to exceed the amount of exercise
	Less than 10 minutes of each	Mild	1
	10 to 29 minutes of each	Mild	2
Combination of cardio and strength exercises	30 to 59 minutes of each	Mild	4
	60 to 120 minutes of each	Mild	6
	More than 120 minutes, but less than 240 minutes of each	Mild	8
	More than 240 minutes of each	Mild	8 points and send a message not to exceed the amount of exercise
	Less than 10 minutes of each	Moderate	2
	10 to 29 minutes of each	Moderate	4
	30 to 59 minutes of each	Moderate	6
	60 to 120 minutes of each	Moderate	8
	More than 120 minutes, but less than 240 minutes of each	Moderate	10
	More than 240 minutes of each	Moderate	8 points and send a message not to exceed the amount of exercise
	Less than 10 minutes of each	Intense	4
	10 to 29 minutes of each	Intense	8
	30 to 59 minutes of each	Intense	16
	60 to 120 minutes of each	Intense	24
	More than 120 minutes, but less than 240 minutes of each	Intense	32
	More than 240 minutes of each	Intense	32 points and send a message not to exceed the amount of exercise

Table SM1.3. Scores according to the frequency of food consumption by groups

Food group	Points for consumption frequency	Score
Mexican food and dishes	Once a week	1
	2 times a week	2
	3 times a week	3
	4 times a week	4
	5 times a week	5
	6 times a week	6
	7 times a week	7
	< once a week	0
Mexican desserts and drinks	Once a week	1
	2 times a week	0
	3 times a week	0
	4 times a week	0
	5 times a week	0
	6 times a week	0
	7 times a week	0
	Once a week	1
Fruits, vegetables, legumes, dairy, seeds and healthy fats, eggs	2 times a week	2
	3 times a week	3
	4 times a week	4
	5 times a week	5
	6 times a week	6
	7 times a week	7
	< once a week	0
	Once a week	3
Fish and shellfish, chicken and other white meats	2 times a week	2
	3 times a week	1
	4 times a week	0
	5 times a week	0
	6 times a week	0
	7 times a week	0
	0 times a week	7
	Once a week	1
Red and processed meats, Ultra-processed foods, Foods high in sugars, trans and saturated fats	2 times a week	0
	3 times a week	0
	4 times a week	0
	5 times a week	0
	6 times a week	0
	7 times a week	0
	Once a week	1

Table SM1.4. Scores by frequency of consumption

Food group	Consumption quantities	Score
Mexican foods and dishes, fruits, vegetables, legumes, dairy products, seeds and healthy fats, eggs	< recommended portion or > minimum portion	1
	Recommended portion	2
	< recommended maximum or > recommended portion	1
	> the recommended maximum or < the recommended minimum	0
Fish and shellfish, chicken and other white meats, Red and processed meats, Ultra-processed foods, Foods high in sugars, trans and saturated fats	Minimum portion	3
	< Recommended portion > minimum portion	2
	> recommended portion < maximum portion	1
	> Maximum portion	-1

Note: recommend amount of consumption will be determined by the linear optimization programming. An example is shown in Table SM1.5.

Table SM1.5. Examples of recommended amounts of consumption by food groups including the target foods of the intervention

Consumption	Group by objective	Food	Examples of amounts of consumption		
			Average Recommended Serving	Range	Minimum
Daily (at least 1 food from the group)	Mexican food and dishes	Chilaquiles with or without egg and/or chicken	1 cup (160 g)	80 g	240 g
		Mexican style egg (tomato, onion, chili, nopal)	1 plate (220 g)	110 g	330 g
		Quesadilla of corn tortilla (without meat)	1 piece (60 g)	30 g	90 g
		Beans taco	1 piece (60 g)	30 g	90 g
		Panela cheese and beans torta (not meat)	1 piece (197 g)	98.5	295.5 g
		Chicken tamal (no red meat)	1 piece (200 g)	100 g	300 g
		Tamal of ash, chard, or cheese (without red meat)	1 piece (200 g)	100 g	300 g
		Sweet tamal (corn, fruits)	1 piece (172 g)	86 g	258 g
		Mole with chicken	1 plate (334 g)	167 g	501 g
		Chicken or vegetarian (mushroom) pozole	1 plate (300 g)	150 g	450 g
		Chicken or cheese flute (no red meat)	1 piece (75 g)	37.5 g	112.5 g
		Bean or chicken sope (no red meat)	1 piece (75 g)	37.5 g	112.5 g
		Chicken or cheese enchilada (no red meat)	1 piece (75 g)	196.5 g	589.5 g
		Fish or chicken taco (no beef or pork)	1 piece (75 g)	37.5 g	112.5 g
		Bean burrito (no meat)	1 piece (100 g)	50 g	150 g
		Fresh water without sugar	1 cup (240 ml)	120 ml	360 ml
		Toast with beans or chicken	1 big toast (174 g)	87 g	261 g
		Rice pudding	½ cup (178 g)	89 g	267 g
1 time per week		Flan	1 piece (120 ml)	60 ml	180 ml
		Capirotada	1 slice (60 g)	30 g	90 g
		Sweet bread	1 piece (63 g)	31.5 g	94.5 g
		Atole in water	1 cup (240 ml)	120 ml	360 ml
		Atole in milk or champurrado	1 cup (240 ml)	120 ml	360 ml
		Tejuino	2 cups (418 ml)	209 ml	627 ml
		Tuba	1 cup (240 ml)	120 ml	360 ml
		Tepache or honey water	1 cup (240 ml)	120 ml	360 ml

Note: this table will be updated according to the linear optimization programming.

Table SM1.5. Continuation: Examples of recommended amounts of consumption by food groups including the target foods of the intervention

Consumption	Group by objective	Food	Examples of amounts of consumption	
			Average Recommended Serving	Range
Daily (at least 1 food from the group)	Fruits	Papaya	1 cup (140 g)	70 g 210 g
		Tuna	1 piece (70 g)	35 g 105 g
		Pineapple	1 cup (165 g)	82.5 g 247.5 g
		Soursop	½ piece (175 g)	87.5 g 262.5 g
		Guava	2 pieces (83 g)	41.5 g 124.5 g
		Capulín	1 cup (32 g)	16 g 48 g
		Pitaya	1 piece (50 g)	25 g 75 g
		Nance	5 pieces (15 g)	7.5 g 22.5 g
		Creole plum	2 pieces (105 g)	52.5 g 157.5 g
		Zucchini	1 piece (91 g)	45.5 g 136.5 g
Daily (at least 1 food from the group)	Vegetables	Pumpkin	½ cup (110 g)	55 g 165 g
		Onion	½ cup (58 g)	29 g 87 g
		Mushrooms	1 cup (93 g)	46.5 g 139.5 g
		Chayote	½ cup (80 g)	40 g 120 g
		Spicy chili	1 cup (30 g)	15 g 45 g
		Huitlacoche	1/3 cup (66 g)	33 g 99 g
		Tomato	2 pieces (124 g)	62 g 186 g
		Nopales	2 pieces (134 g)	67 g 201 g
		Bell pepper	1 piece (64 g)	32 g 96 g
		Poblano chili	1/2 piece (32 g)	16 g 48 g
Daily (at least 1 food from the group)	Whole grains	Quelites	½ cup (66 g)	33 g 99 g
		Green tomato	5 pieces (86 g)	43 g 129 g
		Purslane	1 cup (115 g)	57.5 g 172.5 g
		Corn tortilla	1 piece (30 g)	15 g 45 g
		Baked corn toast	2 pieces (20 g)	10 g 30 g
		Corn dough	1 ball (45 g)	22.5 g 67.5 g
		Unsweetened amaranth	¼ cup (16 g)	8 g 24 g
		Sweetened amaranth	¼ cup (16 g)	8 g 24 g
		Sweet potato	1/3 cup (69 g)	34.5 g 103.5 g

Note: this table will be updated according to the linear optimization programming.

Table SM1.5. Continuation: Examples of recommended amounts of consumption by food groups including the target foods of the intervention

Consumption	Group by objective	Food	Examples of amounts of consumption		
			Average Recommended Serving	Range	
Daily (at least 1 food from the group)	Legumes	Pot beans	½ cup (86 g)	43 g	129 g
		Fried beans	1/3 cup (75 g)	37.5 g	112.5 g
		Cooked lentils	½ cup (99 g)	49.5 g	148.5 g
		Cooked chickpeas	½ cup (82 g)	41 g	123 g
		Baked beans	½ cup (85 g)	42.5 g	127.5 g
Daily (at least 1 food from the group)	Dairy products	Curd	3 tablespoons (36 g)	18 g	54 g
		Fresh cheese	1 slice (40 g)	20 g	60 g
		Panela cheese	1 slice (40 g)	20 g	60 g
		Natural yogurt	1 cup (227 g)	113.5 g	340.5
		Whole milk	1 cup (240 ml)	120 ml	360 ml
		Semi-skimmed milk	1 cup (240 ml)	120 ml	360 ml
Daily (at least 1 food from the group)	Seeds and healthy fats	Skim milk (light)	1 cup (240 ml)	120 ml	360 ml
		Avocado	1/3 piece (31 g)	15.5 g	46.5 g
		Dried beans	¼ cup (38 g)	19 g	57 g
		Pumpkin seeds	2 tablespoons (15 g)	7.5 g	22.5 g
		Chia seeds	5 teaspoons (12 g)	6 g	18 g
		Peanuts	14 pieces (12 g)	6 g	18 g
Daily (at least 1 food from the group)	Eggs	Canola oil	1 teaspoon (5 g)	5 ml	15 ml
		Complete chicken egg	1 piece (44 g)	22 g	66 g
		Egg white	2 pieces (66 g)	33 g	99 g
0 to 3 times a week	Fish and shellfish	White fish	1 portion (40 g)	0 g	60 g
		Octopus	1 portion (25 g)	0 g	37.5 g
		River prawn	4 pieces (110 g)	0 g	165 g
0 to 3 times a week	Chicken and other white meat	Grilled chicken	1 portion (29 g)	0 g	58 g
		Chicken in piece	1/3 piece (29 g)	0 g	58 g
		Insects (maguey worms, crickets)	1 portion (35 g)	0 g	52.5 g

Note: this table will be updated according to the linear optimization programming.

Table SM1.5. Continuation: Examples of recommended amounts of consumption by food groups including the target foods of the intervention

Consumption	Group by objective	Food	Examples of amounts of consumption	
			Average Recommended Serving	Range
0 to 1 time a week	Red and processed meats	Beef	1 portion (14 g)	0 g 60 g
		Pork Meat	1 portion (14 g)	0 g 60 g
		Rabbit	1 portion (29 g)	0 g 58 g
		Pork or turkey ham	1 slice (10.5 g)	0 g 21 g
		Pork or turkey sausage	1 slice (14 g)	0 g 60 g
		Longaniza, chorizo, pepperoni or salami	1 portion (14 g)	0 g 30 g
		Beef or pork tacos	1 piece (75 g)	0 g 112.5 g
		Quesadilla with meat, gringa or synchronized (with sausages or meats)	1 piece (60 g)	0 g 90 g
		Enchilada with beef or pork	1 piece (75 g)	0 g 112.5 g
		Flute with beef or pork	1 piece (75 g)	0 g 112.5 g
		Sope with beef or pork	1 piece (75 g)	0 g 112.5 g
		Pork pozole	1 plate (300 g)	0 g 450 g
		Offal	1 plate (300 g)	0 g 450 g
		Birria	1 plate (200 g)	
0 to 1 time a week	Ultra-processed foods	Meat tamal	1 piece (200 g)	0 g 300 g
		Torta (marinated, meat, drowned)	1 piece (197 g)	0 g 295.5 g
		Beef burrito	1 piece (100 g)	0 g 150 g
		Toast with beef or pork	1 large piece of toast (174 g)	0 g 261 g
		Soft drink with sugar	1/4 can (92 ml)	0 ml 138 ml
		Sugar free soft drink	1/4 can (92 ml)	0 ml 138 ml
		Packaged juice	1/3 cup (80 ml)	0 ml 120 ml
		Packaged cookies	1 piece (10.5 g)	0 g 15.75 g

Note: this table will be updated according to the linear optimization programming.

Table SM1.5. Continuation: Examples of recommended amounts of consumption by food groups including the target foods of the intervention

Consumption	Group by objective	Food	Examples of amounts of consumption	
			Average Recommended Serving	Range
0 to 1 time a week	Foods high in added and free sugars, trans and saturated fats	Table sugar to sweeten	1 teaspoon (4 g)	0 g 6 g
		Fresh water with sugar	1 cup (240 ml)	0 g 360 ml
		Industrialized jams	1 tablespoon (17 g)	0 g 25.5 g
		Industrialized syrups and honeys	1 teaspoon (7 g)	0 g 10.5 g
		Cake or pie (thin slice)	1 slice (28 g)	0 g 32 g
		Vegetable oil (not olive or canola)	1 teaspoon (5 ml)	0 g 7.5 ml
		Salt added to already prepared foods	1 pinch (2 g)	0 g 3 g
		Vegetable shortening	1 teaspoon (5 g)	0 g 7.5 g
		Margarine	1 teaspoon (5 g)	0 g 7.5 g
		Lard	1 teaspoon (5 g)	0 g 7.5 g
		Butter	1 teaspoon (5 g)	0 g 7.5 g

Note: this table will be updated according to the linear optimization programming.

Supplementary Material 2. Inclusion, exclusion, and elimination criteria

Table SM2.1. Inclusion, exclusion, and elimination criteria

Study Criteria		
Inclusion	Exclusion	Elimination
Being between 18 and 35 years old	Not signing the informed consent	Not completing the questionnaires
Being Mexican	Not accepting to donate blood and/or stool samples	Do not allow the extraction of blood and / or delivery of stool sample
Reside in the South of Jalisco for at least 1 year	Not being able to stand up to take anthropometric data	Failure to complete the 7-week intervention or 7-week follow-up
Levels of physical activity below what is recommended and what is established as a criterion for inclusion in the study (Table SM2)	Perform levels of physical activity above the minimum established as criteria for inclusion in the study (Table SM2)	
Consuming amounts of food below or above that established as criteria for inclusion in the study or in a lesser or greater frequency than recommended, according to the type of food (Table SM2)	Consume adequate levels of the foods to be promoted in the intervention program (Table SM2)	
Have a Smartphone	Being pregnant or lactating	
Not having consumed antibiotics at least 3 months before the intervention	Suffer from a chronic disease such as type 2 diabetes mellitus, arterial hypertension, dyslipidemia, under medication	
Have a BMI between 18.5 and 40	Suffering from an autoimmune disease such as type 1 diabetes, hypo or hyperthyroidism	
Not having a medical diagnosis of chronic disease under pharmacological treatment	Having a gastrointestinal disease such as Crohn's disease, ulcerative colitis, etc.	
Not having a medical diagnosis of gastrointestinal disease	Having used antibiotics less than 3 months ago	
	Taking antidepressant medications or corticosteroids	
	Consume probiotics or nutritional supplements, except protein powder	

Table SM2.2 Cut-off points to establish inadequate consumption and physical activity, to be included in the research

Physical activity	Inclusion criteria	
	Light	
	< 3 times per week	< 30 minutes per day
Type of physical activity		
Weekly frequency		
Minutes per day		
Food group	Consumption to be included in the study	Frequency of consumption to be included in the study
Mexican food and dishes	< 100 g p ⁻¹ d ⁻¹	< 7 times a week
Fruits	< 400 g p ⁻¹ d ⁻¹	< 7 times a week
Vegetables	< 400 g p ⁻¹ d ⁻¹	< 7 times a week
Whole cereals	< 200 g p ⁻¹ d ⁻¹	< 7 times a week
Legumes	< 60 g p ⁻¹ d ⁻¹	< 7 times a week
Seeds and healthy fats	< 80 g p ⁻¹ d ⁻¹	< 7 times a week
Dairy products	> 250 ml p ⁻¹ d ⁻¹	> 5 times a week
Eggs	> 25 g p ⁻¹ d ⁻¹	> 5 times a week
Fish and shellfish	> 28 g p ⁻¹ d ⁻¹	> 3 times a week
Chicken	> 29 g p ⁻¹ d ⁻¹	> 3 times a week
Red and processed meats	> 7 g p ⁻¹ d ⁻¹	> once a week
Ultra-processed foods	> 10 g p ⁻¹ d ⁻¹	> once a week
Added and free sugars and foods high in trans and saturated fats	> 31 g p ⁻¹ d ⁻¹	> once a week

Supplementary Material 3. Clinical history which will be uploaded to the mobile application

Table SM3.1 Initial Assessment Questionnaire

Clinic history				
General and sociodemographic data				
Last name:	Middle name:	Name:		
Cell phone:	Email:			
Age:	Date of Birth:			
Sex:	Country of birth:			
City of residence:	State of birth:			
Time living there:	Occupation			
Less than 1 month	Officer, director or boss			
1 to 6 months	Professional or technician			
6 to 12 months	Auxiliary worker in administrative activities			
1 to 3 years	Merchant, sales clerk, or sales agent			
3 to 6 years	Workers in personal and surveillance services			
6 to 9 years	Worker in agricultural, livestock, forestry, hunting or fishing activities			
10 years or more	Craft worker			
Lifetime	Industrial machinery operator, assemblers, chauffeur or transport driver			
	Workers in elementary and support activities			
Education				
Did not study	Student			
Unfinished primary	Unemployed			
Finished elementary school	Retired			
Unfinished high school	Other (specify):			
High school finished	Days a week that work			
Unfinished high school	1			
School completed	2			
Unfinished technical career	3			
Technical career finished	4			
Undergraduate student	5			
Unfinished degree	6			
Completed bachelor's degree	7			
Master's degree	Modality			
Doctorate	Face-to-face			
Specialty	Online			
Other:	Mixed			
Individual and family monthly income (pesos per month MXN)	Individual expenditure on food per month (MXN pesos)	Household expenditure on food per month (MXN pesos)	Feeding	
-0 - 2,699		0 - 500	Favorite foods	
2,7 - 0 - 6,799	-0 - 200	500 - 1,000		
6,8 - 0 - 11,599	2-0 - 500	1,000 - 3,000	Foods you don't like	
11,6 - 0 - 34,999	500 - 800	3,000 - 6,000		
35,000 - 84,999	800 - 1,000	6,000 - 9,000	Food allergies and intolerances	
+ 85,000	1,500- 2,000	10,0-0 - 13,000	Lactose	
	2,500 - 3,000	13,000 - 16,000	Seafood	
	3,000 - 3,500	16,000 - 20,000	Gluten	
	+ 4,000	+ 20,000	Fresas	
Diet and physical activity				
Main place of food purchase	Who cooks the food you eat?	Are you currently following a specific diet?		
Tianguis	Me		Nuts	
Market	Mother	Yes	Peanuts	
Retail supermarket (Soriana, Walmart)	Father	To lose weight		
Wholesale supermarket (Sam's, Costco)	Economic Kitchen	To gain weight		
Butcher shop	Restaurants	Ketogenic		
Creamery	I get it as a gift	Vegetarian (ovo-lacto, ovo or lacto)		
Fruit store	Others (specify):	Intermittent fasting		
Others (specify):		Vegan		
		Mediterranean		
		DASH or diet to stop hypertension		
		Others (specify):		

Table SM3.1 Continuation: Initial Assessment Questionnaire

Clinic history			
Physical activity			
Currently doing physical activity			Type of activity
Less than 3 times a week			Walking
3 or more days of vigorous activity of at least 20 minutes per day			Jogging
5 or more days of moderate to vigorous activity or walking at least 30 minutes per day			Run
3 days a week of very vigorous activity for at least 60 minutes a day			Aerobics, Zumba or dance
7 days a week of moderate to vigorous activity or even walking for at least 60 minutes per day			Cycling
Times a week		Type of activity	Swimming
1			Crossfit
2			Weightlifting
3			Multifunctional
4			Focused exercises (write which ones, e.g. sit-ups, sit-ups, push-ups)
5			Other:
6			
7			
Intensity		120	
Mild		150	
Moderate		180	
Intense		210	
		240 or more	
		Other:	
Anthropometric data			
Estimated weight for you:		Size in centimeters estimated by you:	
Height (centimeters):		Weight (kg):	BMI:
Fat percentage:		Muscle mass:	Body water:
Metabolic age:		Metabolic rate:	Visceral fat:
Waist circumference:		Hip circumference:	Bone mass:
Biochemical indicators		Clinical indicators	
Fasting glucose		Blood pressure	
Glucose 2 hours after eating		Acanthosis nigricans	
Triglycerides		Signs and symptoms of nutritional deficiencies	
Total cholesterol		Overall status	
LDL cholesterol		Very tired	
HDL cholesterol		Dizziness	
Gut microbiota		Very thirsty	
Gastrointestinal signs and symptoms			
Abdominal swelling		Frequent urination	
How often does it happen?		Very hungry	
Diarrhea		Do your feet or hands swell?	
How often does it happen?		What time of day does it occur?	
Constipation		How often does it happen?	
How often does it happen?		How many hours do you spend sitting a day?	
Reflux		How many hours do you spend standing a day?	
How often does it happen?		Nose bleed	
Abdominal swelling		How often does it happen?	
